Enhancing the Acceptability of Psychological Treatments for
Obsessive-Compulsive Disorder

Study Protocol and Statistical Analysis Plan

Unique Protocol ID: 30006258

Date: July 20, 2018

Study Protocol

Individuals who contact the clinic expressing interest in the study will first complete a telephone screen in order to assess their potential eligibility. Screener questions from the ADIS-V will be used to determine their likely inclusion in the study; those who seem likely to be eligible will be invited to the clinic to complete a baseline assessment, consisting of the ADIS-V and YBOCS, as well as measures of OCD, anxious and depressive symptomatology and demographic and treatment history measures.

We will administer several measures to assess treatment acceptability. These will include the Credibility/Expectancy Questionnaire (CEQ), and the Treatment Acceptability / Adherence Scale (TAAS). The CEQ and TAAS will serve as subjective measures; objective measures will include counts of treatment refusers and dropouts across the two treatments. A refuser is defined as a participant who is deemed eligible following the initial assessment, but who declines to continue at any time after randomization, but before session 2 (the first session is for case formulation, treatment planning, and includes a comprehensive description of the treatment approach). A dropout is defined as a participant who withdraws their participation from the study any time after the beginning of session 2. Should any participant refuse or drop out of CT or ERP, we will ask them to list their reasons for this decision.

In addition to the Anxiety Disorders Interview Schedule (ADIS-V), we will administer the Yale-Brown Obsessive-Compulsive Checklist (YBOCS). Diagnostic and interview reliability will be assessed via a second trained rater who will listen to and rate recordings of interviews. In instances where there is disagreement on diagnostic status, a team meeting will be held to discuss the issues and resolve the discrepancy. Self-report measures assessing OCD symptoms (i.e., Vancouver Obsessional Compulsive Inventory, VOCl), OCD beliefs (Obsessional Beliefs Questionnaire, OBQ), process measures (e.g., Personal Significance Scale, PSS), as well as measures of depression and anxiety symptomatology (Beck Depression Inventory, 2nd Ed, BDI & Beck Anxiety Inventory, BAI) will be administered.

Eligible participants will be block randomized (to ensure equal numbers of participants per treatment condition) via www.randomizer.org, and will begin session 1 of either ERP or CT with one of 2 therapists (see below). Participants will be asked to complete the PSS and VOCl before the start of each session. At all time points, assessors will be blind to treatment assignment, such that they will not know whether a participant has been offered or is receiving ERP or CT. After the 3rd, 6th, and 12th and final session, and at each follow- up point, participants will be asked to complete the CEQ and TAAS in order to assess their views of the acceptability of the treatment they receive. After session 6, participants will complete a mid-therapy assessment consisting of the YBOCS, VOCl, OBQ, PSS, BAI and BDI.

This RCT will involve trial administration (shared by the Investigators and the study coordinator), an assessment team (research assistant and graduate student), and a team of 3 therapists (post-doctoral fellow(s) and a senior graduate student). This will allow for comparisons of therapist effects, as well as the effects of therapist experience on outcome and acceptability. The first 6 months of the project are reserved for training team members on relevant tasks. Training will be overseen by the NPA, and offered by all project investigators.

ERP (12 sessions) will be based on a standard, commonly-used manual, and will comprise 1 session of case formulation and treatment planning, 10 sessions of ERP, plus 1 final session on relapse prevention. Exposures in this protocol are prolonged and repeated, requiring clients/patients to engage in a series of exposures to feared stimuli (e.g., contaminants, doubts, intrusive thoughts), and to refrain from engaging in compulsive behaviour until their anxiety subsides. ERP is well-established, and known to be highly effective for OCD.

CT (12 sessions) will be modularized, and based on elements from our three primary treatment packages. It will begin with 1 session of case formulation and treatment planning, followed by 10 sessions focused on evidence gathering and behavioural experiments (which are importantly different from prolonged exposure), plus 1 final session on relapse prevention. The 3 treatment packages share a number of common features – they include focus on reducing inflated responsibility, target the personal significance of the participant's thoughts or compulsions, etc. Each also incorporates other elements specific to the primary symptom (e.g., beliefs about memory in compulsive checking, a perceived violation in mental contamination, or thought-action fusion in association with obsessions), allowing CT to be tailored to the individual beliefs and concerns of each participant. Many of these cognitive areas of focus are highly novel, and have not been assessed in previously conducted RCT's of CT, although our focus on problematic beliefs and appraisals in general is entirely consistent with established CT for OCD packages.

All sessions will be recorded in situ for the purposes of assessing treatment fidelity; this will be done on an ongoing basis via trained coders, blind to hypotheses and to condition assignment who will be asked to assess the proportion of session content allocated to a focus on behaviour/exposure vs. cognition/reappraisal. Audio recording devices will be made available to participants and their use is a standard enhancement of treatment interventions to help make them more memorable, and to clarify any questions that may arise between sessions.

At the end of treatment, and at 6- and 12-month follow-up periods, participants will complete the mid-therapy assessment measures again, in addition to the ADIS-V.

Statistical Plan

Primary hypotheses will be tested by comparing our indices of acceptability across the two treatments. Specifically, participant ratings of treatment acceptability, and the relative numbers of treatment refusers and dropouts will be assessed. Independent samples *t*-tests will be used to compare the two treatments groups on self-reported treatment acceptability on the CEQ and the TAAS. Furthermore, chi-squared tests will be used to compare treatments on the number of refusers and drop outs.

Completer and intent-to-treat analyses will be conducted on YBOCS and VOCI total scores (i.e., OCD symptom severity) measured at multiple time points. ANCOVA will compare treatments on changes in OCD symptom severity across all measurement periods, with baseline scores as covariates. Although we have reason to suspect that our CT may outperform more traditional cognitive approaches to the treatment of OCD, we expect that both ERP and CT will be similarly effective (as has been shown in numerous trials, and in a recent comprehensive review), perhaps with intent-to-treat analyses showing a small advantage of CT over ERP, yet we do not expect to be powered to detect significant differences.

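### The dropout definition counts leaving the study, with no end point, instead of stopping therapy, so it misclassifies participants in a primary comparison

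*Combined protocol and SAP*

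**What the plan says.** The Study Protocol's account of the acceptability measures says that "objective measures will include counts of treatment refusers and dropouts across the two treatments". It then gives the only definition of the second count: "A dropout is defined as a participant who withdraws their participation from the study any time after the beginning of session 2". The refuser definition just before it has a window closed at both ends, from randomization to session 2. The next sentence speaks of leaving a therapy: "Should any participant refuse or drop out of CT or ERP, we will ask them to list their reasons for this decision".

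Both therapies have 12 sessions. Participation does not stop there: "At the end of treatment, and at 6- and 12-month follow-up periods, participants will complete the mid-therapy assessment measures again". The CEQ and TAAS are also collected after therapy: "After the 3rd, 6th, and 12th and final session, and at each follow- up point".

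Under Statistical Plan, "Primary hypotheses will be tested by comparing our indices of acceptability across the two treatments", and for the counts "chi-squared tests will be used to compare treatments on the number of refusers and drop outs".

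**The concern.** The count is meant to show how acceptable each treatment is. The defined event, however, is withdrawal from the study, and its window opens at session 2 and never closes. The neighbouring sentences speak of treatment, so two concepts are in use, and no other section says which is counted. The same participant can be a dropout under one wording and not under the other.

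At stake is one of the primary comparisons. Follow-up withdrawals at the same rate in both arms dilute a real difference in therapy dropout. Withdrawals at different rates can hide a real difference or create a false one. The CEQ and TAAS comparisons do not depend on this definition.

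**Working it through.** **Reading the rule.** Two cases separate the concepts.

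| Participant | Stopped therapy? | Dropout under the written rule? |
|---|---|---|
| Completes session 12, withdraws before the 12-month visit | No | Yes |
| Stops at session 5, stays for assessments | Yes | No |

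The rule gives the wrong answer in both cases if the aim is to measure acceptance of the treatment.

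**Inputs for the size.** The documents give 1:1 allocation and the chi-squared test. They give no sample size, alpha, power or dropout rate, so there is no figure of the plan's own to reproduce. Everything below is assumed: 60 or 100 participants per arm reaching session 2, a two-sided 5% test, and these rates:

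- d = proportion stopping therapy
- f = proportion of therapy completers who later withdraw
- g = share of therapy-stoppers who stay in the study and are not counted

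**Formulas.** Recorded proportion = d(1 − g) + (1 − d)f. With g and f equal in the two arms, the recorded difference is (d₁ − d₂)(1 − g − f). Power is for the two-proportion test, with pooled variance under the null and unpooled under the alternative, both tails.

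**(a) Equal follow-up withdrawal.** d = 20% ERP and 10% CT, g = 0. For example, f = 5% gives 0.20 + 0.80 × 0.05 = 24.0% and 0.10 + 0.90 × 0.05 = 14.5%.

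| f | Recorded ERP vs CT | Difference (points) | Power, 60 per arm | Power, 100 per arm |
|---|---|---|---|---|
| 0% | 20.0% vs 10.0% | 10.0 | 33% | 51% |
| 2% | 21.6% vs 11.8% | 9.8 | 30% | 46% |
| 5% | 24.0% vs 14.5% | 9.5 | 26% | 40% |
| 10% | 28.0% vs 19.0% | 9.0 | 21% | 32% |
| 15% | 32.0% vs 23.5% | 8.5 | 18% | 27% |
| 25% | 40.0% vs 32.5% | 7.5 | 14% | 20% |

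Simulation of the uncorrected chi-squared test (400,000 runs) at f = 0, 5%, 15% and 25% agreed to within about 1 percentage point.

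**(b) Unequal follow-up withdrawal, real difference.** Same d, g = 0.

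- f = 5% ERP, 15% CT: 24.0% vs 0.10 + 0.90 × 0.15 = 23.5%. The 10-point difference falls to 0.5.
- f = 15% ERP, 5% CT: 0.20 + 0.80 × 0.15 = 32.0% vs 14.5%. The difference inflates to 17.5 points.

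**(c) Unequal follow-up withdrawal, no real difference.** d = 15% in both arms, g = 0.

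- f = 5% vs 15%: 0.15 + 0.85 × 0.05 = 19.25% vs 0.15 + 0.85 × 0.15 = 27.75%. The chance of a significant result rises from 5% to 19% (60 per arm) or 29% (100 per arm).
- f = 5% vs 8%: 19.25% vs 0.15 + 0.85 × 0.08 = 21.8%. The chance is about 6% or 7%.

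**(d) Therapy-stoppers who stay in the study.** d = 20% and 10%, g = 25%, f = 5%: 0.20 × 0.75 + 0.80 × 0.05 = 19.0% vs 0.10 × 0.75 + 0.90 × 0.05 = 12.0%. The difference is 7.0 points, with power of 18% or 28%.

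**Check with other rates.** With therapy dropout of 30% vs 15%, g = 20% and f = 10%, the recorded rates are 31% vs 20.5%. The difference falls from 15 to 10.5 points, and power at 100 per arm falls from 72% to 40%.

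**The case against.** The best defence is that the meaning is plain from context. The paragraph speaks of treatment refusers and of leaving CT or ERP, and refusal and dropout divide at a point on the therapy timeline. A sensible coder would probably count people who leave therapy. That is a fair account of the likely intent. But the one explicit definition says something else, and a coder who follows it exactly gets a different count.

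Second, no section describes people who stop therapy and stay for assessments. If stopping therapy in practice ends participation, that group is empty. This stands: the omission is conditional, and the 25% in case (d) has no source. The text does not exclude the group, and the planned intent-to-treat analysis of symptoms is compatible with it. The other half, completers who withdraw later, does not depend on this.

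Third, the size may be small. The rule requires active withdrawal, so a missed visit alone need not count. At f = 2% the loss is slight, and a mild imbalance of 5% vs 8% barely raises the false-positive rate. The 5% vs 15% scenarios are deliberately strong. Power is also low under the therapy-based definition at these assumed sizes, which is a separate matter. All of this limits the likely impact but does not make the rule correct.

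Finally, acceptability ratings are collected at follow-up, so later behaviour is not wholly foreign to the construct. That is a weak argument for merging it with therapy dropout. Withdrawal after session 12 can be reported separately.

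**Conclusion.** The definition is wrong as written for its stated purpose. It counts full-therapy completers who later withdraw, it leaves out any therapy-stoppers who remain in the study, and it feeds a primary test. That conclusion rests on the text alone and is firm.

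The size is uncertain, because every rate and sample size used here is an assumption. Rare and balanced follow-up withdrawal would cost little. Common withdrawal would dilute the comparison materially, and a large imbalance between arms could reverse its message. The documents do not show how participants were in fact counted. The definition should be corrected, because the change is cheap and the count is a primary index.

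**What to change.** Define a dropout as a participant who stops the assigned therapy between the start of session 2 and the end of session 12, whether or not they formally withdraw or remain in the study. Report withdrawal after the end of therapy separately, by arm, as loss to follow-up.

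Two details belong with the definition. State in advance how non-attendance is classified as having stopped therapy. Report by arm those who ended early because of improvement or were withdrawn by the study team, since neither is evidence of unacceptability. The plan already asks dropouts for their reasons, which helps with the first group.

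The core change is one sentence, with a little more for these details. No new data collection is needed to establish the last session attended: "All sessions will be recorded in situ for the purposes of assessing treatment fidelity". The dropout count will change and may be smaller, because follow-up withdrawals leave it while therapy-stoppers who stay in the study enter it.

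### CEQ and TAAS are first scheduled after session 3, so refusers and the earliest dropouts have no acceptability rating scheduled before they leave

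*Combined protocol and SAP*

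**What the plan says.** The Study Protocol names CEQ and TAAS as the subjective measures of acceptability, and counts of refusers and dropouts as the objective ones. The scales are scheduled thus: "After the 3rd, 6th, and 12th and final session, and at each follow- up point, participants will be asked to complete the CEQ and TAAS". The stated purpose is "in order to assess their views of the acceptability of the treatment they receive".

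No earlier occasion is listed. The baseline assessment is described as "consisting of the ADIS-V and YBOCS, as well as measures of OCD, anxious and depressive symptomatology and demographic and treatment history measures". The per-session measures are two other scales: "Participants will be asked to complete the PSS and VOCl before the start of each session".

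A refuser is an eligible participant who "declines to continue at any time after randomization, but before session 2". A dropout is one who "withdraws their participation from the study any time after the beginning of session 2". Of session 1 the protocol says: "the first session is for case formulation, treatment planning, and includes a comprehensive description of the treatment approach". On leaving, the only request described is this: "Should any participant refuse or drop out of CT or ERP, we will ask them to list their reasons for this decision".

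The Statistical Plan puts both kinds of index under the primary hypotheses: independent-samples t-tests for CEQ and TAAS, and chi-squared tests for refusers and dropouts. For the t-tests it gives no time point, analysis set or missing-data rule. Completer and intent-to-treat analyses are named for the YBOCS and VOCI totals only.

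**The concern.** The people most likely to find a treatment unacceptable are plausible early leavers, and session 1 gives them the description on which to decide. If they go before anyone asks for a rating, the t-tests on the scales can draw only on those who stayed. Randomisation balances the groups at allocation; it does not balance those still present after session 3 if staying depends on how acceptable the assigned treatment seemed.

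Two things are at stake. The rating difference between arms could be distorted. The two sets of primary results could also appear to disagree, for example with more refusals in one arm but similar ratings among those who remain, and the plan does not say how that would be read. A rating not collected at the time cannot be recovered at analysis.

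**Working it through.** **Step 1: the timeline.** Setting the definitions beside the schedule, both from the Study Protocol:

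| Point of leaving | Status | CEQ/TAAS scheduled before leaving? |
|---|---|---|
| After randomisation, before session 1 | Refuser | No |
| After session 1, before session 2 | Refuser | No |
| From the start of session 2 to the end of session 3 | Dropout | No |
| After the session 3 rating | Dropout | Yes, at least one |

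The first three rows cover every refuser and the earliest dropouts. If the t-tests use a time point later than session 3, dropouts between session 3 and that point may be missing too.

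**Step 2: could follow-up ratings fill the gap?** Both scales are also planned at follow-up. A dropout is defined as withdrawing from the study, which makes later ratings unlikely. A refuser is defined only as declining to continue, so that wording does not settle the matter for refusers. The documents do not say that either group is followed up.

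**Step 3: how large could the effect be?** The documents give no loss rate, SD or expected difference for these scales, so there is no stated figure to reproduce. All inputs below are assumptions.

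Let the rating have SD 1 among all randomised participants. Let a normal latent leaving propensity have correlation r with the rating, such that lower raters tend to leave, and let a share p of the arm leave before the analysed rating. The mean among stayers then rises by r × L(p), where L(p) = φ(z_p)/(1 − p), z_p is the p-quantile of the standard normal and φ its density. So

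difference seen = true difference + r_CT × L(p_CT) − r_ERP × L(p_ERP).

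Values: L(0.05) = 0.109, L(0.10) = 0.195, L(0.15) = 0.274, L(0.25) = 0.424, L(0.30) = 0.497.

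With a true difference of 0.50 SD in favour of CT and the same r in both arms:

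| Loss CT / ERP | r | Calculation | Difference seen |
|---|---|---|---|
| 5% / 10% | 0.3 | 0.50 + 0.3 × (0.109 − 0.195) | 0.474 |
| 15% / 25% | 0.3 | 0.50 + 0.3 × (0.274 − 0.424) | 0.455 |
| 5% / 15% | 0.5 | 0.50 + 0.5 × (0.109 − 0.274) | 0.417 |
| 10% / 30% | 0.5 | 0.50 + 0.5 × (0.195 − 0.497) | 0.349 |
| Equal loss | any, equal | the two terms cancel | 0.50 |
| Any | 0 | both terms are zero | 0.50 |

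Divided by the stayers' SD instead, the first four rows become 0.48, 0.46, 0.43 and 0.37.

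**Step 4: is the direction fixed?** Only under a common r. If r differs by arm, say CT 15% loss with r = 0.7 and ERP 25% loss with r = 0.3, the difference seen is 0.50 + 0.192 − 0.127 = 0.565 SD, larger than the truth although ERP loses more people. Nothing in the documents supports these particular correlations; the example shows only that the sign is not determined.

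**The case against.** The strongest reply is that the scales are meant to capture views of the treatment received. A refuser has had at most formulation, planning and a description, so a rating of treatment received is barely defined for that person. Refusal and dropout have their own primary tests, so leavers do count in the primary evidence. This largely stands. It makes a comparison among people who reached a given session a coherent quantity, provided that it is labelled as such. It does not turn that comparison into one of the randomised groups, and someone who leaves during session 2 or 3 has received some treatment without being asked to rate it.

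A second reply is that silence on the analysis set does not establish an available-case analysis, and that selection needs some participants actually to leave early. Both points are right. A reader might infer that the t-tests are certain to compare selected groups, or are known to be biased, perhaps against CT. The documents support neither: they give no loss rates, and the analysis set is unspecified.

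A reader might also infer that no leaver can ever supply a rating. That goes too far. Follow-up of refusers is neither promised nor excluded, and the paragraph introducing the scales gives no timing. What the text does show is that no rating is scheduled before these participants leave.

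Finally, the effect is modest in most of the assumed cases: the 0.35 SD result needs 30% of one arm gone before the analysed rating. That also stands.

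**Conclusion.** The schedule gap is in the text. All refusers, and any dropouts before the end of session 3, have no CEQ or TAAS rating scheduled before they leave. The consequence is conditional: if some participants leave before the analysed rating and only available ratings are used, the primary t-tests would compare groups selected after randomisation by events that the plan treats as measures of acceptability.

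Size and direction of any bias are unknown. Under the assumed normal selection model with a common correlation, a true 0.50 SD difference appears as about 0.46 to 0.47 SD in mild cases and 0.35 SD in a severe one, with no bias in the mean difference under equal loss and equal correlation, or under zero correlation. The chi-squared comparisons do not depend on these ratings. The point is worth acting on because it touches a primary comparison and is inexpensive to address.

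**What to change.** Keep the existing rating occasions and make these changes:

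- Add CEQ and TAAS at the end of session 1, after the treatment has been described and before the participant leaves the visit.
- Pre-specify a between-arm comparison of the session 1 ratings in all randomised participants who have them, labelled as expected acceptability.
- Separately, name one later time point for the acceptability of the treatment received. Do not pool session 1 ratings into that analysis as if they were the same outcome. State that it applies to participants who reached that point, and read it together with the refusal and dropout counts.
- State which of the two comparisons is primary.
- Limit any sensitivity analysis for missing later ratings to participants who began the treatment sessions (session 2 onward), so that nobody is assigned a rating of treatment they never started.
- Report by arm how many participants lack each rating.

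The cost is a few minutes per participant, with questionnaires already in use at a visit that already takes place, and two more pre-specified comparisons, one per scale. Completing an acceptability questionnaire at that moment might itself influence refusal; this is possible but not shown. Anyone who leaves before session 1 would still have no rating.

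### The protocol says its therapist team permits a comparison of experience effects, but with one graduate student on the team such a difference cannot be attributed to experience rather than to that person

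*Combined protocol and SAP*

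**What the plan says.** The team paragraph of the Study Protocol lists "a team of 3 therapists (post-doctoral fellow(s) and a senior graduate student" among the trial staff. It follows directly with "This will allow for comparisons of therapist effects, as well as the effects of therapist experience on outcome and acceptability". Experience is thus tied to the make-up of the team. Years of practice, prior OCD cases and cases treated within the trial are not mentioned as measures of it.

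The paragraph on randomisation gives a different headcount: participants "will begin session 1 of either ERP or CT with one of 2 therapists (see below". The same sentence states what is randomised: "Eligible participants will be block randomized (to ensure equal numbers of participants per treatment condition". How participants come to a particular therapist is not described, nor is it said whether each therapist delivers both treatments.

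The Statistical Plan contains no therapist or experience analysis. It opens with "Primary hypotheses will be tested by comparing our indices of acceptability across the two treatments". The t-tests "will be used to compare the two treatments groups on self-reported treatment acceptability on the CEQ and the TAAS"; "chi-squared tests will be used to compare treatments on the number of refusers and drop outs"; and for symptoms, "ANCOVA will compare treatments on changes in OCD symptom severity across all measurement periods, with baseline scores as covariates". Every named test compares treatments.

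**The concern.** The protocol credits the design with a property it does not appear to have. To attribute a difference between therapists to their experience, one needs several therapists at each level, so that variation between individuals of like experience can be set against the difference between levels. Here the less experienced level is one person. That person may differ from the fellows in manner, skill or rapport for reasons unrelated to training stage, and the data would look the same.

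If an experience comparison were reported on the strength of this sentence, a difference between individuals could be presented as a finding about training level, for outcome and for acceptability. Because no analysis is specified, nothing in the plan would guard against the simplest and most misleading version, which pools participants by therapist grade and ignores who treated them.

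**Working it through.** The documents give no sample size, therapist ICC or experience effect, so there is no stated figure to reproduce. The following are assumptions: outcome SD 1; therapist variance equal to the ICC, ρ, from 0 to 0.10; total N of 60, 102 or 138; equal caseloads; two-sided 5% tests. From the documents come three therapists, one of them a graduate student (so two fellows by subtraction), or alternatively two therapists.

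**1. Aliasing (needs none of the assumptions).** With two fellows and one student, the therapist indicators have rank 3. Adding a column for experience leaves the rank at 3. With one fellow and one student it is 2 and stays 2. As a fixed effect, experience is fully aliased with therapist.

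**2. More participants do not help.** With m = N/3 participants per therapist, the variance of the fellow-minus-student contrast is

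ρ(1/2 + 1) + (1 − ρ)(1/(2m) + 1/m) = 1.5ρ + 4.5(1 − ρ)/N.

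Only the second term falls with N. At ρ = 0.05 and N = 60 the variance is 0.075 + 0.07125 = 0.14625, so the SE is 0.382. The SE is 0.333 at N = 120 and 0.276 at N = 3,000, and it cannot fall below √0.075 = 0.274. The floor √(1.5ρ) is 0.122, 0.173, 0.274 and 0.387 SD at ρ = 0.01, 0.02, 0.05 and 0.10.

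**3. Test with therapists as units.** Degrees of freedom are the number of therapists minus 2.
- Two therapists: 0 df, so no test exists.
- Three therapists: 1 df, critical t = 12.706. Power follows from the noncentral t with noncentrality δ/SE, for a true difference δ.

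| ρ | Power, δ = 0.5 SD (N = 60 / 102 / 138) | Power, δ = 0.8 SD (N = 60 / 102 / 138) |
|---|---|---|
| 0 | 11.6 / 14.9 / 17.2% | 18.1 / 23.5 / 27.2% |
| 0.01 | 10.7 / 13.0 / 14.4% | 16.7 / 20.4 / 22.7% |
| 0.02 | 10.0 / 11.7 / 12.6% | 15.5 / 18.3 / 19.9% |
| 0.05 | 8.7 / 9.5 / 9.9% | 13.1 / 14.6 / 15.3% |
| 0.10 | 7.6 / 8.0 / 8.1% | 10.9 / 11.6 / 11.9% |

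Over the whole assumed range, power is about 8-17% for 0.5 SD and 11-27% for 0.8 SD. With unlimited participants the power for 0.5 SD would still be only 25%, 12% and 9% at ρ = 0.01, 0.05 and 0.10.

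**4. Participant-level test that ignores therapist, no true experience effect.** The three-therapist rates are simulated. The two-therapist rates are exact: 2·P(t(N−2) > t_crit/√(1 + nρ/(1 − ρ))) with n = N/2. For example, at N = 138 and ρ = 0.10 the divisor is √(1 + 69 × 0.10/0.90) = 2.94, which gives 50.3%.

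| ρ | False positives, 3 therapists (N = 60 / 102 / 138) | False positives, 2 therapists (N = 60 / 102 / 138) |
|---|---|---|
| 0 | 5.0 / 5.0 / 5.0% | 5.0 / 5.0 / 5.0% |
| 0.01 | 7.2 / 9.0 / 10.4% | 8.5 / 11.0 / 13.1% |
| 0.02 | 9.6 / 13.0 / 15.6% | 12.0 / 16.8 / 20.5% |
| 0.05 | 16.4 / 23.4 / 28.3% | 21.8 / 30.4 / 36.0% |
| 0.10 | 26.1 / 35.8 / 41.6% | 34.0 / 44.4 / 50.3% |

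For any ρ above 0, a larger trial makes the false attribution more likely.

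**5. Effect on ERP versus CT.** With therapists assigned by chance, the planned two-group t-test rejected a true null in 4.7-5.2% of simulated trials (two or three therapists; ρ = 0.02, 0.05, 0.10; 30, 51 or 69 per arm). For a model with an intercept, arm and two therapist indicators, the rank is 4 of 4 when therapists are crossed with arms and 3 of 4 when they are nested.

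**The case against.** The strongest reply is that no experience test is planned. The sentence sits in a staffing paragraph, the Statistical Plan compares treatments throughout, and the false-positive rates above belong to a test constructed here for illustration. This stands. It limits the harm to what might be reported beyond the plan, and the size of that harm depends on ICC and N values that the documents do not give. At ICC 0 the participant-level test keeps its 5% level.

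A second reply is that three therapists do allow a valid test. This also stands formally. A reader might infer that an experience effect is untestable under any model; that is too strong, since it holds for fixed therapist effects and for the two-therapist reading only. But the 1-df test takes its whole estimate of therapist variation from two fellows, has very low power, and still has one person at the student level.

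Third, the headcount is partly inferred. The wording would permit a single fellow, with the third therapist unspecified, and the protocol never defines experience as student versus fellow. However, any split of three people into two levels leaves one level with a single person, and replacing a fellow would not add a second student. Experience counted as cases treated in the trial could vary within a therapist, but no such measure is defined.

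Finally, comparing these particular therapists with one another remains possible. That half of the sentence is not disputed.

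**Conclusion.** The point holds for the experience claim. One named student and no other measure of experience mean that a student-versus-fellow difference cannot be attributed to experience, whatever the number of participants. That conclusion rests on the staffing description alone. The numerical consequences rest on the assumed ICC (0-0.10), N (60-138) and equal caseloads: power of 8-17% or 11-27% for the valid three-therapist test, no test with two therapists, and false positives of 5% to 42% (three therapists) or 5% to 50% (two) if therapist is ignored.

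A reader might go on to infer that the ERP-versus-CT comparison is compromised. The documents do not support that. The primary hypotheses concern acceptability by treatment, do not use the experience claim, and keep their level under chance assignment of therapists. The two headcounts, the unstated assignment to therapists and the unstated crossing with arms are gaps to be clarified; they do not show that therapists were nested in arms. Nor would nesting make every therapist contrast inestimable. With three therapists, one arm would have two, and they could be compared; what would be lost is a treatment effect adjusted for fixed therapist effects.

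This is worth correcting because the protocol asserts something the design cannot deliver, but the harm is confined to a secondary claim.

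**What to change.** Delete the statement that effects of experience can be compared. Alternatively, restate it as a descriptive summary of results by therapist, saying that the student level is one person and that no inference about experience will be drawn. Keep all planned primary tests as they are.

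In the same edit:
- reconcile the two therapist headcounts;
- state how participants are assigned to therapists and whether each therapist delivers both ERP and CT;
- commit to a table of therapist-by-arm counts.

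If therapists are crossed with treatment, a therapist-adjusted model may be added as a sensitivity analysis only. If they are nested in arms, state as a limitation that a treatment effect adjusted for fixed therapist effects cannot be estimated.

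The cost is a few sentences and one table, with no extra staff or participants. The trial gives up only a secondary claim it could not support. The optional model requires the treating therapist to be recorded, and participants who refuse before meeting a therapist would be missing from it.
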